6.2.6. Endpoints for immunogenicity data of avelumab

All analyses described below are performed for Arm A only.

Blood samples for avelumab immunogenicity testing will be collected within 2 hours before the start of the avelumab infusion on Day 1, Day 15 and Day 29 of Cycle 1, on Day 1 and Day 29 of Cycles 2-4, on Day 1 of Cycle 6, and then every 2 cycles thereafter. An additional sample must be collected at 30 days after the last dose of avelumab.

Samples positive for ADA will be analyzed for titer and may be analyzed for nAb. As of the finalization of this SAP, the nAb assay is not yet available, therefore the analyses of nAb data described in the following sections will only be conducted contingent upon assay and data availability at the time of reporting.

Patients will be characterized into different ADA categories based on the criteria defined in Table 15.

Table 15 Patients Characterized Based on Anti-Drug Antibody Results (ADA Status)

Category	Definition	Subjects at Risk (Denominator for Incidence)
ADA never-positive	No positive ADA results at any time point; ADA-negative patients (titer < cutpoint)	Number of patients with at least one valid ADA result at any time point
ADA ever-positive	At least one positive ADA result at any time point; ADA-positive patients (titer ≥ cutpoint)	Number of patients with at least one valid ADA result at any time point
Baseline ADA positive	A positive ADA result at baseline	Number of patients with valid baseline ADA result
Treatment-boosted ADA	A positive ADA result at baseline and the titer ≥ 8×baseline titer at least once after treatment with avelumab	Number of patients with valid baseline ADA results and at least one valid post-baseline ADA result
Treatment-induced ADA	Patient is ADA-negative at baseline and has at least one positive post-baseline ADA result; or if patient does not have a baseline sample, the patient has at least one positive past-baseline ADA result	Number of patients with at least one valid post-baseline ADA result and without positive baseline ADA result (including missing, NR)
Transient ADA response	If patients with treatment-induced ADA have (a single positive ADA result or duration between first and last positive result <16 weeks) and ADA result at the last assessment is not positive.	Number of patients with at least one valid post-baseline ADA result and without positive baseline ADA result (including missing, NR)

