Persistent ADA response	If patients with treatment-induced ADA have duration between first and last positive ADA result ≥16 weeks or a positive ADA result at the last assessment	Number of patients with at least one valid post-baseline ADA result and without positive baseline ADA result (including missing, NR)

ADA: anti-drug antibody, NR = not reportable.

Patients will be characterized into different nAb categories based on the criteria in Table 16. For nAb, treatment-boosted is not applicable since no titer result is available.

Table 16 Patients Characterized Based on Neutralizing Antibody Results (nAb Status)

Category	Definition	Subjects at Risk (Denominator for Incidence)
nAb never-positive	No positive nAb results at any time point	Number of patients with at least one valid ADA result at any time point
nAb ever-positive	At least one positive nAb result at any time point	Number of patients with at least one valid ADA result at any time point
Baseline nAb positive	A positive nAb result at baseline	Number of patients with valid baseline ADA result
Treatment-induced nAb	Patient is not nAb positive at baseline and has at least one positive post-baseline nAb result; or if patient does not have a baseline sample, the patient has at least one positive post-baseline ADA result	Number of patients with at least one valid post-baseline ADA result and without positive baseline nAb result (including missing, NR)
Transient nAb response	If patients with treatment-induced nAb have (a single positive nAb result or duration between first and last positive result <16 weeks) and nAb result at the last assessment is not positive.	Number of patients with at least one ADA valid post-baseline result and without positive baseline nAb result (including missing, NR)
Persistent nAb response	If patients with treatment-induced nAb have duration between first and last positive nAb result ≥16 weeks or a positive nAb result at the last assessment	Number of patients with at least one valid post-baseline ADA result and without positive baseline nAb result (including missing, NR)

ADA = antidrug antibody, nAb = neutralizing antibody, NR = no result.

The number and percentage of patients in each ADA and nAb category will be summarized.

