6.2.6.1. Time to and Duration of ADA and nAb response

The ADA and nAb analyses described below will include patients with treatment-induced ADA or nAb, respectively.

Time (weeks) to ADA response is defined as:

$$(\text{Date of first positive ADA result} - \text{date of first dose of avelumab} + 1)/7.$$

Time to ADA response will be summarized using simple descriptive statistics (mean, SD, median, min, max, Q1, Q3).

Duration (weeks) of ADA response is defined as:

$$(\text{Date of last positive ADA result} - \text{date of first positive ADA result} + 1)/7.$$

Duration of ADA response will be censored if:

- the last ADA assessment is positive AND patient is ongoing treatment with avelumab, or

- the last ADA assessment is positive AND patient discontinued treatment with avelumab AND the last planned ADA assessment (30 days after the last dose of avelumab) is after the cut-off date.

Time to nAb response and duration of nAb response are defined similarly based on first and last positive nAb result.

Kaplan-Meier estimates (product-limit estimates) will be presented together with a summary of associated statistics including the median ADA response time with 2-sided 95% CIs. ADA response rates at different timepoints will be estimated with corresponding 2-sided 95% CIs. The CIs for the median will be calculated according to Brookmeyer and Crowley (1982) and the CIs for the survival function estimates will be derived using the log-log transformation according to Kalbfleisch and Prentice (2011) (confotype=loglog default option in SAS Proc LIFETEST) with back transformation to a CI on the untransformed scale. The estimate of the standard error will be computed using Greenwood's formula.

Duration of ADA response will be displayed graphically and analyzed using Kaplan-Meier methodology. If the number of patients with ADA response is small, the Kaplan-Meier method may not provide reliable estimates. In this case, only descriptive statistics or listings will be provided

As data permit, the analyses described above will be repeated for patients with treatment-induced nAb.

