6.2.6.3. Analysis of PK, safety and efficacy by immunogenicity status

The following ADA and nAb status will be used for the analyses described below.

ADA

- ADA ever-positive versus ADA never-positive
- ADA: treatment-induced ADA versus ADA never-positive or baseline ADA positive

nAb

- nAb ever-positive versus nAb never-positive
- nAb: treatment-induced nAb versus nAb never-positive or baseline nAb positive

Data listings will include immunogenicity data together with relevant PK, safety and efficacy data.

PK parameters and immunogenicity status

The following analyses will include patients in both the immunogenicity analysis set and in the PK parameter analysis set. The PK endpoint pertinent to the immunogenicity analyses is C_{trough} .

Blood samples for avelumab PK will be collected pre-dose on Day 1, Day 15 and Day 29 of Cycle 1, on Day 1 and Day 29 of Cycles 2-4, Day 1 of Cycle 6, every 2 cycles after Cycle 6, and 1 month after end of avelumab treatment.

C_{trough} will be summarized descriptively (n, mean, SD, CV, median, minimum, maximum, geometric mean, its associated CV, and 95% CI) by nominal time and ADA status. Linear-linear and log-linear plots of mean and median for C_{trough} over nominal time and by ADA status will be presented.

Among patients with treatment-induced ADA, analyses will be conducted to assess whether C_{trough} has any changes before and after the first positive ADA assessment. To be included in this analysis, patients must have the same PK parameter available both before and after the first positive ADA assessment. Relative PK day will be calculated as:

$$(\text{PK assessment nominal day}) - (\text{first positive ADA assessment nominal day}).$$

Nominal day is the protocol scheduled timing for an assessment. For example, if C_{trough} is collected on Day 1 of Cycle 2 and the first positive ADA result is observed on Day 1 of Cycle 3, then the relative PK day for this C_{trough} is -42. Linear-linear and log-linear plots of mean and median for C_{trough} over relative PK day will be presented.

As data permit, the analyses described above will be repeated for nAb.

Safety and immunogenicity status

The following analyses will include patients in the immunogenicity analysis set.

The frequency (number and percentage) of patients with each of the following will be presented by ADA status.

- TEAEs, by SOC and PT
- TEAEs leading to dose reduction of avelumab, by SOC and PT

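### SAP Table 16 lets a positive ADA result alone define treatment-induced nAb when the baseline sample is missing, so a patient with no positive nAb result can be counted as treatment-induced nAb and as nAb never-positive

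*SAP*

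**What the plan says.** SAP section 6.2.6 treats nAb as a second step after ADA: "Samples positive for ADA will be analyzed for titer and may be analyzed for nAb". It adds that the nAb assay was not available when the SAP was finalised, and that nAb analyses depend on the assay and data being available at reporting.

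Table 16 then gives treatment-induced nAb two alternative conditions:

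- Limb 1: "Patient is not nAb positive at baseline and has at least one positive post-baseline nAb result".
- Limb 2: "if patient does not have a baseline sample, the patient has at least one positive post-baseline ADA result".

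The treatment-induced ADA row of Table 15 has a nearly identical second limb: "if patient does not have a baseline sample, the patient has at least one positive past-baseline ADA result".

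The nAb never-positive row of Table 16 reads "No positive nAb results at any time point". The denominator for treatment-induced nAb includes patients whose baseline nAb result is missing or not available.

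Two later sections use the category. Section 6.2.6.1 restricts the nAb time and duration analyses to patients with treatment-induced nAb, and states: "Time to nAb response and duration of nAb response are defined similarly based on first and last positive nAb result". Section 6.2.6.3 lists two nAb contrasts for the by-status analyses. One is ever-positive against never-positive. The other is "nAb: treatment-induced nAb versus nAb never-positive or baseline nAb positive".

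The protocol (section 9.3.2, Immunogenicity Assessment) asks for the percentage of patients positive for ADA and for neutralizing antibodies. It does not define treatment-induced nAb, so nothing there overrides Table 16.

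**The concern.** One category rests on two different markers. An ADA result is the right criterion in Table 15. In Table 16 it admits patients for whom no neutralizing antibody has been shown, because their ADA-positive sample was nAb-negative or was never tested for nAb.

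Table 16 then contradicts itself. Treatment-induced nAb should be a subset of nAb ever-positive, and as written it need not be. At stake are the reported incidence of treatment-induced nAb and the trough-concentration and safety summaries that use the second nAb contrast. The time-to and duration-of-response analyses would also formally include patients who have no nAb dates. Immunogenicity of avelumab is a stated secondary objective, and nAb is named in its endpoint.

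**Working it through.** The plan states no incidence or sample size for nAb, so there is no figure to reproduce. The check is to classify every possible patient type under the rule as written, and again with nAb in limb 2.

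**Step 1. Enumerate.** A later positive nAb result is possible only if the patient is ADA-positive, because only ADA-positive samples are tested. That leaves nine types.

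| Baseline sample | Baseline nAb | Later ADA | Later nAb positive | Treatment-induced, as written | Treatment-induced, nAb in limb 2 | nAb never-positive |
|---|---|---|---|---|---|---|
| missing | – | neg | no | no | no | yes |
| **missing** | **–** | **pos** | **no** | **yes** | **no** | **yes** |
| missing | – | pos | yes | yes | yes | no |
| present | neg | neg | no | no | no | yes |
| present | neg | pos | no | no | no | yes |
| present | neg | pos | yes | yes | yes | no |
| present | pos | neg | no | no | no | no |
| present | pos | pos | no | no | no | no |
| present | pos | pos | yes | no | no | no |

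Exactly one of the nine types changes: baseline missing, later ADA-positive, no positive nAb. It is also the only type that is both treatment-induced and never-positive.

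**Step 2. Follow that patient through the SAP.**

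- Table 16 incidence: counted in the numerator. The patient is already in the denominator, which allows a missing baseline.
- Table 16 transient and persistent rows: both need positive nAb results, so the patient meets neither. The two rows need not add up to the treatment-induced total.
- Section 6.2.6.1: in the analysis set, but with no first or last positive nAb date, so time and duration are undefined.
- Section 6.2.6.3, treatment-induced contrast: on both sides, for the trough-concentration and safety summaries.
- Section 6.2.6.3, change in trough concentration around the first positive result, and timing of infusion reactions, when repeated for nAb: both need a first positive nAb assessment, which does not exist.
- Section 6.2.6.3, ever-positive against never-positive: correctly placed as never-positive.
- Section 6.2.6.3, efficacy: a listing and a line plot for ADA ever-positive patients, with nAb dates only where applicable. Neither is split by treatment-induced nAb.

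**Step 3. Rough size.** The SAP plans about 830 patients randomized 1:1, so Arm A has about 830 / 2 = 415. The other rates are assumptions and are not in the documents: baseline sample missing m = 1% to 5%; later ADA-positive a = 5% to 20%; of those, no positive nAb q = 50% to 100%.

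Misclassified patients = 415 × m × a × q:

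- 415 × 0.01 × 0.05 × 0.5 = 0.10 (0.025% of Arm A)
- 415 × 0.05 × 0.05 × 0.5 = 0.52 (0.125%)
- 415 × 0.01 × 0.20 × 1.0 = 0.83 (0.2%)
- 415 × 0.05 × 0.20 × 1.0 = 4.15 (1.0%)

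**The case against.** The wording might be deliberate. The denominators in Table 16 also use valid ADA results, and a sponsor might choose a conservative rule where the baseline is unknown. The denominators are coherent, since a patient who is ADA-negative needs no nAb test, but that does not justify an ADA criterion in the numerator. A conservative rule would also be expected in limb 1. Moreover, if limb 1 is read to include a missing baseline, as the denominator does, the only patients limb 2 adds are those with no positive nAb result.

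The stronger part of the objection concerns reach, and it stands. A reader might infer that ADA-positive, nAb-negative patients in general are counted as nAb-positive. They are not: those with a baseline sample are classified correctly, and the ever-positive row still requires a positive nAb result. A reader might also infer that efficacy results by nAb status are distorted, but section 6.2.6.3 contains no efficacy summary by treatment-induced nAb. Nor would spurious times or durations be reported, because an affected patient has no nAb date to contribute.

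It also stands that few patients should qualify. A pre-dose sample is scheduled for Cycle 1 Day 1. SAP section 3.4.1 takes the last assessment before avelumab as baseline, and presumes that a planned same-day sample with no recorded time was taken before dosing. The nAb analyses may also never be run.

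**Conclusion.** The point holds as a definition error at the lowest severity. Limb 2 of treatment-induced nAb names the wrong marker, most likely carried over from Table 15, and no other text corrects it. One patient type is misclassified: no baseline sample, ADA-positive later, no positive nAb result. The effects are an inflated treatment-induced nAb incidence, double membership in one of the two nAb contrasts, and undefined entries in the time and duration set.

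The classification error follows from the SAP text alone. Its size, about 0.1 to 4.2 patients or up to 1.0 percentage point of incidence, rests on the assumed rates shown above and gives only an order of magnitude. The analysis is descriptive, confined to Arm A and contingent on the nAb assay. The primary and alpha-controlled secondary tests are not touched.

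**What to change.** In the treatment-induced nAb row of Table 16, replace ADA with nAb in the second limb, so that a patient without a baseline sample also needs a positive post-baseline nAb result. Leave the ADA-based denominators as they are. The cost is one word. Of the nine patient types only the misclassified one changes, and the overlaps and undefined values listed above disappear. No data collection or other analysis is affected. The change is best made before any nAb tables are specified.

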6.2.6.1. Time to and Duration of ADA and nAb response

The ADA and nAb analyses described below will include patients with treatment-induced ADA or nAb, respectively.

Time (weeks) to ADA response is defined as:

$$(\text{Date of first positive ADA result} - \text{date of first dose of avelumab} + 1)/7.$$

Time to ADA response will be summarized using simple descriptive statistics (mean, SD, median, min, max, Q1, Q3).

Duration (weeks) of ADA response is defined as:

$$(\text{Date of last positive ADA result} - \text{date of first positive ADA result} + 1)/7.$$

Duration of ADA response will be censored if:

- the last ADA assessment is positive AND patient is ongoing treatment with avelumab, or

- the last ADA assessment is positive AND patient discontinued treatment with avelumab AND the last planned ADA assessment (30 days after the last dose of avelumab) is after the cut-off date.

Time to nAb response and duration of nAb response are defined similarly based on first and last positive nAb result.

Kaplan-Meier estimates (product-limit estimates) will be presented together with a summary of associated statistics including the median ADA response time with 2-sided 95% CIs. ADA response rates at different timepoints will be estimated with corresponding 2-sided 95% CIs. The CIs for the median will be calculated according to Brookmeyer and Crowley (1982) and the CIs for the survival function estimates will be derived using the log-log transformation according to Kalbfleisch and Prentice (2011) (confotype=loglog default option in SAS Proc LIFETEST) with back transformation to a CI on the untransformed scale. The estimate of the standard error will be computed using Greenwood's formula.

Duration of ADA response will be displayed graphically and analyzed using Kaplan-Meier methodology. If the number of patients with ADA response is small, the Kaplan-Meier method may not provide reliable estimates. In this case, only descriptive statistics or listings will be provided

As data permit, the analyses described above will be repeated for patients with treatment-induced nAb.

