24. **Pharmacokinetics for avelumab:** In Arm A only, pre-dose PK samples for avelumab (3.5 mL) will be taken on Day 1, Day 15 and Day 29 of Cycle 1, on Day 1 and Day 29 of Cycles 2-4, Day 1 of Cycle 6 and then every 2 cycles thereafter up to Cycle 16. Pre-dose samples can be taken up to 2 hours prior to the start of avelumab infusion. Details are outlined in Section 7.3.

26. **Mandatory Archival FFPE Tumor Tissue:** An archival formalin fixed, paraffin embedded (FFPE) tumor tissue block from primary diagnosis specimen must be provided for all patients enrolled in the study and submitted to the Central Laboratory prior to randomization. [REDACTED] Cytology samples (eg, FFPE cell pellet from Fine Needle Aspiration biopsy) are not acceptable. See [Section 6.1.1](#) and [Section 7.5.1](#).

27. **Mandatory Recent FFPE Tumor Tissue Block:** A baseline de novo tumor biopsy (biopsied tumor lesion should not be a RECIST target lesion) must be obtained for all patients enrolled. [REDACTED] For baseline de novo biopsy, tumor tissue from cytologic sampling (eg, fine needle aspiration, including FFPE cell pellet material), is not adequate and should not be submitted. The de novo biopsy(ies) should be formalin-fixed and paraffin-embedded as per routine (see Study Manual), and the resulting FFPE tissue block(s) should be submitted to the Central Laboratory. [REDACTED] See [Section 6.1.1](#) and [Section 7.5.1](#).

28. **Anti-Avelumab Antibodies (Anti-Drug Antibodies, ADAs) and Neutralizing Antibodies (Nab).** In Arm A one blood sample (3.5 mL) for anti-avelumab antibodies will be collected pre-dose at Day 1, Day 15 and Day 29 of Cycle 1, at Day 1 and Day 29 of Cycles 2-4 at Day 1 of Cycle 6, and then every 2 cycles thereafter up to Cycle 16. All samples should be drawn within 2 hours before start of avelumab infusion. All the samples that are positive for ADA may also undergo characterization for Nab. See [Section 7.4](#).

29. **MUGA Scan or ECHO.** For the evaluation of the left ventricular ejection fraction, the technique used at screening will be consistently used throughout the study, in the following assessments.

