17. **Survival Assessment:** All patients will be followed for survival and subsequent anticancer therapies every 3 months ( $\pm 14$  days) until death, end of the study or patient withdrawal of consent, whichever comes first. Information will be collected by telephone call unless the patient is visiting the site for other reasons. The Sponsor will request an "ad hoc" survival update prior to each protocol-specified interim analysis and final analysis. The investigator or designee must make every effort to collect the patient's status through contacting the patient or a relative or their usual health care provider by telephone or other allowed methods. These contact attempts should be documented in the patient's medical record.
18. **Patient-Reported Outcome Questionnaire:** FKSI-19 and EUROQoL 5-Dimension (EQ-5D) are to be administered at the End of Treatment/Withdrawal visit. PROs should be administered prior to other End of Treatment/Withdrawal measures. Beyond End of Treatment (ie, follow-up period), PRO assessments will be collected at the same time a tumor assessment is performed.
19. **Pharmacokinetics:** In Arm A, PK blood samples for avelumab (3.5 mL) will be taken 1 month after end of avelumab treatment. Details are outlined in Section 7.3.
- [REDACTED]
21. **De Novo Tumor Biopsy:** A *de novo* (ie, fresh biopsy) tumor sample should also be collected at End of Treatment/Withdrawal visit, unless clinically contraindicated. Tumor tissue from cytologic sampling (eg, fine needle aspiration, including FFPE cell pellet material), is not adequate and should not be submitted. The *de novo* biopsy(ies) should be formalin-fixed and paraffin-embedded as per routine (see Study Manual), [REDACTED] should be submitted to the Central Laboratory. See [Section 7.5.1](#).
22. **Anti-Avelumab Antibodies (Anti-Drug Antibodies, ADAs) and Neutralizing Antibodies (Nab):** In Arm A, one blood sample (3.5 mL) for anti-avelumab antibodies (and simultaneous pharmacokinetic draws for measurement of avelumab) will be collected at 30 days after the end of avelumab treatment. All the samples that are positive for ADA may also undergo characterization for Nab. See [Section 7.4](#).
23. **MUGA Scan or ECHO.** For the evaluation of the left ventricular ejection fraction, the technique used at screening will be consistently used throughout the study, in the following assessments.

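### In the Kaplan-Meier analysis of ADA duration, patients off avelumab and still ADA-positive at their last sample count as events, so the curve can only be too low

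*SAP*

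**What the plan says.** SAP 6.2.6.1 covers Arm A patients with treatment-induced ADA. Duration in weeks is the date of the last positive result minus the date of the first, plus one day, divided by 7. The analysis is Kaplan-Meier, with a median and rates at time points. Where responders are few, descriptive statistics or listings replace it.

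There are two censoring conditions. The first is "the last ADA assessment is positive AND patient is ongoing treatment with avelumab, or" the second, which needs a positive last result, avelumab discontinued, and that "the last planned ADA assessment (30 days after the last dose of avelumab) is after the cut-off date". Neutralizing antibody (nAb) duration is defined in the same way.

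On sampling, SAP 6.2.6 states: "An additional sample must be collected at 30 days after the last dose of avelumab". Footnote 22 of the protocol's follow-up Schedule of Activities agrees that the sample "will be collected at 30 days after the end of avelumab treatment". Neither place plans a later ADA draw.

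SAP Table 15 classes a treatment-induced patient as having a persistent response if first and last positives are at least 16 weeks apart "or a positive ADA result at the last assessment".

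**The concern.** A Kaplan-Meier estimate of duration needs an observed end. Here, for some patients, the end of sampling stands in for the end of the response. Their final result is positive, nobody saw them turn negative, and they still enter as completed durations.

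What is at stake is how the immunogenicity tables are read. The median and the rates will be taken as describing how long ADA lasts, or what share of patients are still positive at a given time. The same patients appear in the neighboring table as persistent responders.

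**Working it through.** The documents state no figure for ADA duration, so there is none to reproduce. The check has three parts.

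**1. Who is censored.** Applying SAP 6.2.6.1 to every patient whose last ADA result is positive:

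| Situation | Status under the SAP | Negative result seen? |
|---|---|---|
| On avelumab | Censored | No |
| Off avelumab, 30-day sample due after the cut-off | Censored | No |
| Off avelumab, 30-day sample due by the cut-off and positive | Event | No |
| Off avelumab, 30-day sample due by the cut-off but missed, earlier sample positive | Event | No |

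The SAP does not call the last two rows events. It follows from their falling outside both censoring conditions in a Kaplan-Meier analysis. Suppose two patients were each positive on treatment. If the cut-off falls 29 days after the last dose, the first is censored. If the second gives a day-30 sample and it is positive, that patient is an event. The extra positive result changes censored into finished.

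The extreme case is a first positive at the 30-day sample. The duration is (0 + 1)/7 = 0.14 weeks, counted as complete, and Table 15 calls the response persistent.

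**2. Direction.** At time u, with n at risk and d events, the Kaplan-Meier factor is 1 − d/n. Recoding one patient censored at u as an event gives 1 − (d + 1)/n with n unchanged. The curve is the same before u and never higher from u on. The median and rates can therefore only fall or stay the same.

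**3. Size, by illustration only.** Every rate below is assumed.

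*Ten patients.* Three clear (durations 8, 12, 16 weeks), four are off avelumab and positive at the final sample (20, 24, 28, 32), and three are ongoing (36, 40, 44). SAP rule: the curve goes 0.9, 0.8, 0.7, 0.6, then 0.5 at week 24 and 0.4 at week 28. The median is 24 weeks and the 30-week rate 0.40. With the four censored, the curve stays at 0.70 and the median is not reached.

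*Thirty patients.* Ten clear at 6 weeks. Twenty are off avelumab and last-positive, spread evenly over 10 to 60 weeks. SAP rule: the median is the 15th ordered time, the 5th of the twenty, about 10 + 50 × 5/21 = 21.9 weeks. With the twenty censored, the curve stops at 20/30 = 0.67 and the median is not reached.

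*Simulation on the protocol's sampling schedule.* Samples run from Cycle 1 to Cycle 16, plus the 30-day sample. ADA onset is uniform over weeks 0 to 24, exposure and ADA duration are exponential, and the cut-off falls 52 to 130 weeks after start.

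| Assumed median exposure (weeks) | Assumed true median ADA duration (weeks) | Last-positive but counted as event | Median, SAP rule (weeks) | Median, all last-positive censored (weeks) |
|---|---|---|---|---|
| 26 | 13 | 35% | 6.1 | 10.1 |
| 26 | 26 | 51% | 11.8 | 24.1 |
| 26 | 52 | 63% | 14.8 | 52.1 |
| 26 | never clears | 86% | 24.6 | not reached |
| 52 | 13 | 22% | 8.1 | 10.1 |
| 52 | 26 | 34% | 14.1 | 24.1 |
| 52 | 52 | 43% | 22.2 | 50.1 |
| 52 | never clears | 63% | 49.7 | not reached |

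Censoring does not restore the assumed value in every row (10.1 against 13, 24.1 against 26). Measuring to the last positive sample rather than the first negative one itself shortens duration a little.

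Separately, the protocol's treatment-period footnote 28 limits on-treatment sampling to "every 2 cycles thereafter up to Cycle 16", while SAP 6.2.6 gives no cap. That does not alter the result.

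**The case against.** The strongest defense is that the rule fits the SAP's own definition. Duration runs from first to last positive, not to clearance. It is complete once all planned samples are in, and the two conditions censor when a further planned sample could still extend it. On that view the quantity is observed positivity within the planned sampling window, and an event was never meant to signify loss of ADA.

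This reading is coherent for most patients, but the SAP does not state it. It also fails for the patient who missed the 30-day sample: a planned sample that could have extended the duration was not obtained, and the duration is still taken as complete. Nor does it fit how the output will be read, as a Kaplan-Meier duration of ADA response beside a persistent label. The SAP's own duration of tumor response (6.2.2.7) censors at the last adequate assessment when no progression or death is seen.

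Much of the rest of the defense stands. Patients positive at the last assessment are already counted in Table 15, and SAP 6.2.6.3 lists first and last positive dates and avelumab start and stop for every ever-positive patient. The titer cross-tabulation (6.2.6.2) ignores censoring and is unaffected. Analyses by immunogenicity status use ADA categories, not the curve. The nAb part depends on an assay not available when the SAP was finalized.

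**Conclusion.** The point holds and is worth correcting, with limited reach. If at least one patient is off avelumab, had a 30-day sample due by the cut-off and was last positive, the curve, median and rates are biased short or unchanged, never long. The size is unknown; the figures above rest wholly on assumed inputs. Only a descriptive, Arm A-only summary is affected. No hypothesis test, primary or key secondary result, or titer table changes.

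A reader might infer more than the documents support:

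- *That these responses continue after sampling stops.* Status after the last sample is unknown, which is the reason to censor.
- *That by the later cut-offs almost nobody is censored, or that the curve mainly describes time on avelumab.* The documents give no discontinuation, ADA incidence or clearance rates. In the simulation with a true median of 26 weeks, doubling median exposure moves the SAP-rule median only from 11.8 to 14.1 weeks. It comes close to median exposure only if ADA never clears.
- *That Table 15 and the curve formally contradict each other.* Table 15 admits short persistent responses by design, and would after the fix. The two outputs sit badly together, no more.
- *That a stated objective is compromised.* The objective is to assess immunogenicity. Protocol 9.3.2 offers duration only as a description, subject to the data permitting it.

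**What to change.** Replace the two censoring conditions in SAP 6.2.6.1 with:

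> If the last available ADA (or nAb) result is positive, duration is censored at the date of that result, regardless of avelumab status or cut-off. An event is counted only when a negative result follows the last positive result.

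This is one rule in the SAP and needs no new samples or data. The cost is fewer events and a median that may be reported as not reached. A footnote should say that the estimate assumes the end of sampling is unrelated to how long ADA would have persisted. If the sponsor does want observed positivity within the sampling window, the SAP should say so, label the output that way, and state how a missed 30-day sample is handled.
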